5.5 Criteria for Removal from Study

Patients will be removed from study when any of the criteria listed in Section 5.3 applies. The reason for study removal and the date the patient was removed must be documented in the Case Report Form.

5.6 **Definition of Evaluable Patients**

Patients will be evaluable for the primary endpoint if he or she takes 100% of their capecitabine dose days 1 through 9 and at least 90% of their capecitabine dose days 10 through 15 in cycle one. Unevaluable patients will go off study after cycle 1, but may continue to be treated with commercial capecitabine per the discretion of the treating physician.

6. DOSING DELAYS/DOSE MODIFICATIONS

6.1 General Guidance for Dose Reductions and Modifications

Additional cycles of therapy may be administered provided that the patient meets the following criteria on Day 1 of each cycle:

- ANC \geq 1,000/mcL
- Platelets \geq 75,000/mcL
- Non-hematologic toxicity recovered to \leq grade 1
- No evidence of progressive disease

Dose Modifications: Dose modification for toxicity will be based on the worst toxicity observed during the previous course. Dose modifications apply only when the event(s) are felt to be probably or definitely attributable to the study drugs. After recovery, dose adjustments for toxicity should be applied as below. Patients will be instructed to call with any new or worsening symptoms between clinical evaluations. Held doses will not be made up. All dose modifications will be permanent and continue through subsequent cycles.

Toxicities which are manageable with supportive therapy (ie. antiemetics or anti-diarrhea agents unless occurring despite maximal medical management.) do not require dose reductions. Toxicities which are determined to be clinically insignificant (ie. Lymphopenia) do not require dose reductions.

If an adverse event is not covered in section 6.2, doses may be reduced or held at the discretion of the investigator for the subject's safety.

	Initial Dose	1 st reduction	2 nd reduction
Capecitabine	$1,250 \text{ mg/m}^2$ orally	1,000mg/m ² orally	750mg/m ² orally
	twice daily	twice daily	twice daily

Table 3.	Capecita	abine Dos	e Levels

Dose delays for more than 2 weeks or subjects requiring more than 2 dose reductions will be removed from the study.

6.2 **Dose modifications**

All adverse events will be graded using the NCI Common Terminology Criteria for Adverse Events v4.0.

Hematologic toxicity (Neutropenia, Anemia, Thrombocytopenia): No dose modification for grade 1-2 toxicities. For Grade 3 hematologic toxicity, hold dose until \leq grade 1 or baseline. The may resume capecitabine with dose reduced to the next lower dose level. For grade 4 hematologic toxicity, the patient should discontinue drug and be removed from study. Consider testing for DPD deficiency.

Stomatitis/pharyngitis and other GI toxicities (excluding diarrhea, nausea and

vomiting) For grade 1-2 toxicities, initiate supportive care measures. For grade 3 or 4 toxicities, hold capecitabine until the toxicity returns to \leq grade 1 and then restart capecitabine with a dose reduction to the next lower dose level.

Diarrhea: For grade 1 toxicities, initiate supportive care measures such as loperamide. For grade 2 toxicities, hold capecitabine and give loperamide or other anti-diarrhea medications until \leq grade 1, then resume capecitabine at same dose level. If grade 2 diarrhea occurs a second time at a specific dose level, hold capecitabine and give anti-diarrhea medications until \leq grade 1, then resume capecitabine at the next lower dose level.

For grade 3-4 diarrhea, hold capecitabine, start anti-diarrhea medications, and consider iv fluids/electrolyte replacement. Once resolved to \leq grade 1, then may resume capecitabine at the next lower dose level.

Nausea and vomiting: For grade 1-2 toxicities, initiate supportive care measures such as lorazepam or prochlorperazine. For grade 3-4 toxicities (or intolerable grade 2), hold capecitabine and give antiemetics and consider iv fluids/electrolytes as needed. Once resolved to \leq grade 1, then resume capecitabine at same dose level unless grade 3-4 (or intolerable grade 2) nausea/vomiting occurred despite maximal medical management (at least 2 anti-emetics), then reduce by 1 dose level.

Hepatic Toxicity: For grade 1-2 toxicities, no dose adjustment required. For Grade 3-4 elevation in AST (SGOT), ALT (SGPT), alkaline phosphatase or bilirubin, hold capecitabine dose until \leq grade 1 or back to baseline (whichever is higher). Then may resume capecitabine with dose reduced to the next lower dose level.

Hand-foot reaction (HFR or Palmar-plantar erythrodysesthesia syndrome)**:** Please see table below.

Other toxicity: For other grade 3 or greater toxicities that are considered clinically significant by the treating physician and thought to be at least probably related to study drug, hold treatment until toxicity resolves to grade 1 or less, then reduce the dose of capecitabine to the next lowest dose level.

Table 4: Dose Modifications for HFR or Palmar-plantar erythrodysesthesia syndrome

Skin Toxicity Grade	Occurrence	Suggested Dose Modification
Grade 1: Painless swelling, erythema or discomfort of the hands or feet which does not disrupt the patients normal activity	Any occurrence	Institute supportive measures immediately
Grade 2: Painful erythema and swelling of the hands or feet and/or discomfort affecting the patient's normal activities	1 st occurrence	Institute supportive measures and hold capecitabine until toxicity resolves to Grade 1 or less. Institute at full dose when restarting therapy.
	2 nd or 3 rd occurrence	Continue supportive measures and hold capecitabine until toxicity resolves to Grade 1 or less. Upon resuming capecitabine treatment, decrease capecitabine to next lower dose level
	4 th occurrence	Off study
Grade 3: Moist desquamation, ulceration, blistering or severe pain of the hands or feet, or severe discomfort that causes the patient to be unable to work or perform activities of daily living	1 st occurrence	Institute supportive measures and hold capecitabine treatment for a minimum of 7 days and until toxicity has resolved to Grade 1 or less. When resuming treatment after dose interruption, resume capecitabine at next lower dose level
IIVINg	2 nd occurrence	Institute supportive measures and interrupt capecitabine treatment for a minimum of 7 days and until toxicity has resolved to Grade 1 or less. When resuming treatment after dose interruption, resume capecitabine at next lower dose level
	3 rd occurrence	Off study

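### Section 6.1 exempts manageable diarrhea from dose reduction where the Section 6.2 diarrhea rule reduces the dose, and the Section 6.1 Day 1 criterion has no exception for the grade 2 neuropathy or alopecia allowed at entry

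*Combined protocol and SAP*

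**What the plan says.** **Diarrhea.** Section 6.1 sets a general exemption: "Toxicities which are manageable with supportive therapy (ie. antiemetics or anti-diarrhea agents unless occurring despite maximal medical management.) do not require dose reductions". It sets no grade limit. Section 6.2 then has its own diarrhea rule. For grade 2 it says "If grade 2 diarrhea occurs a second time at a specific dose level, hold capecitabine and give anti-diarrhea medications until" grade 1 or less, and the drug then restarts one level lower. For grade 3-4 it requires a hold, and after recovery the patient "then may resume capecitabine at the next lower dose level". Neither branch asks whether supportive treatment had failed. The nausea and vomiting rule next to it does ask: the dose falls only if the event "occurred despite maximal medical management (at least 2 anti-emetics), then reduce by 1 dose level".

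Three further sentences in 6.1 set the consequences: "After recovery, dose adjustments for toxicity should be applied as below"; "All dose modifications will be permanent and continue through subsequent cycles"; and "Dose delays for more than 2 weeks or subjects requiring more than 2 dose reductions will be removed from the study".

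**Day 1 criterion.** To start a further cycle, 6.1 asks for "Non-hematologic toxicity recovered to" grade 1 or less, with no reference to baseline. Section 3.2.1 admits patients whose grade 2 neuropathy, lymphopenia or alopecia from earlier treatment has not resolved. The hematologic and hepatic rules in 6.2 do accept a return to baseline.

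**The concern.** Two dosing rules for one common toxicity give different answers. The same controlled episode can leave one patient at the starting dose and another on a permanently lower one, depending on which sentence the treating physician follows. It can also change how many reductions count toward removal. For a cytotoxic drug this is a safety matter as well as one of consistency: Section 8.1 warns that capecitabine diarrhea can be severe, and following 6.1 gives the higher dose.

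The Day 1 line raises a smaller question. A patient can be eligible with grade 2 neuropathy or alopecia and then, on a literal reading, fail the condition for starting cycle 2 because of that same finding.

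**Working it through.** The plan states no figure on this point, so the check is a comparison of texts followed by simple arithmetic.

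**Where the diarrhea rules part.** Take an episode that anti-diarrhea drugs bring under control:

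| Episode | 6.1 exemption | 6.2 diarrhea rule | Same dose? |
|---|---|---|---|
| Grade 1 | no reduction required | supportive care | yes |
| First grade 2 at a dose level | no reduction required | hold, restart at same level | yes |
| Second grade 2 at a dose level | no reduction required | hold, restart one level lower | no |
| Grade 3-4, if regarded as manageable | no reduction required | hold, restart one level lower | no |

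The conflict is confined to the last two rows and to the restart dose. The 6.1 sentence speaks of reductions, not holds, so the 6.2 hold applies either way.

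**Size of one step** (Table 3; twice daily for 14 days per cycle):
- First step: 1,000 / 1,250 = 0.80, so 20% lower. Per cycle, 1,250 × 2 × 14 = 35,000 mg/m² against 1,000 × 2 × 14 = 28,000 mg/m².
- Second step: 750 / 1,250 = 0.60, so 40% below the start. Per cycle, 750 × 2 × 14 = 21,000 mg/m².

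**Count toward removal under 6.2.** More than two reductions means removal.
- Grade 3-4 path: episode 1 leads to 1,000, episode 2 to 750, and episode 3 would be the third reduction.
- Grade 2 path, with two episodes at each of three levels: reductions at episodes 2 and 4, and a third at episode 6.
- Under the 6.1 exemption, no reduction is required while the diarrhea stays manageable.

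**How often.** Grade 3-4 diarrhea on capecitabine is 13 + 2 = 15% in Table 1 (colorectal) and 12 + 3 = 15% in Table 2 (breast). With the 10 patients of Section 13.2, 10 × 0.15 = 1.5. This bounds the grade 3-4 branch from above, if those rates carry over to this population, because only manageable episodes are in conflict. The documents give no rate for repeat grade 2 diarrhea.

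**Day 1 criterion.** Neuropathy and alopecia are non-hematologic, so the line reaches them; lymphopenia it does not reach. The sentences in 6.1 on attribution and on clinically insignificant toxicity concern dose modifications and reductions, not starting a cycle. The investigator discretion in 6.1 covers reducing or holding doses. On a literal reading, cycle 2 is due 21 days after the first dose, and removal follows once the delay exceeds 14 days, that is, after 21 + 14 = 35 days.

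**Primary endpoint.** AUC and Cmax are compared between the day 1 and day 9 profiles of cycle 1. The Day 1 list applies from cycle 2, and 6.1 bases modifications on toxicity in the previous course. A hold that breaks the intake rule in 5.6 does so under either reading.

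**The case against.** The best defense is that 6.2 already governs. Section 6.1 is headed as general guidance, sends the reader to the rules that follow it, and gives the investigator discretion over events that 6.2 does not cover, which implies that 6.2 controls those it does. It says that reductions are not required; it does not forbid them, so a physician who follows 6.2 breaches nothing. Grade 3-4 diarrhea that needs a hold and perhaps intravenous fluids may also not count as manageable. Dose adjustments are discussed for each subject at weekly meetings (7.2), which should limit uneven practice.

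Most of this stands, and it makes 6.2 the more natural reading. It does not remove the conflict: 6.1 names anti-diarrhea drugs expressly, and no sentence states outright that the 6.2 diarrhea rule overrides that exemption.

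A reader might infer that the conflict is likely to arise, since 1 − 0.85^10 = 0.80 is the chance of at least one grade 3-4 case in 10 patients. That figure counts every grade 3-4 case, not those where the rules differ, so the documents do not support it as the frequency of conflict.

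On the Day 1 line, the other side says that recovered toxicity in a dosing section naturally means toxicity arising on treatment, and that 3.2.1 attributes the permitted findings to earlier therapy. That is a reasonable reading, but the list does not state it.

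**Conclusion.** The point holds as a wording conflict worth correcting. For a second grade 2 episode at a dose level, or for controlled grade 3-4 diarrhea, the two sections can give 1,250 or 1,000 mg/m² twice daily: a permanent 20% difference that counts toward removal. Its frequency is unknown. For grade 3-4 it is at most 15% if the rates in Tables 1 and 2 apply; for repeat grade 2 there is no figure.

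The Day 1 line is a secondary ambiguity with no rate attached. A reader might infer that it would cost the trial responders. The documents do not support that: they do not say how many patients enter with these findings, whether the findings would persist, or whether a removed patient would have responded. Nor would removal automatically make a patient a response failure, because an off-study scan can still document stable disease.

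The effect is limited to later-cycle dosing, safety and retention. It does not reach the primary pharmacokinetic comparison.

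**What to change.** Make two changes in Section 6.1, in one amendment.

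1. Delete *or anti-diarrhea agents* from the exemption and add: *Diarrhea follows the rule in Section 6.2.* This settles the matter in favor of the specific and more protective rule, and leaves the exemption for antiemetics in line with the nausea rule.
2. Extend the Day 1 line to read: "Non-hematologic toxicity recovered to" *grade 1 or less (except grade 2 neuropathy or alopecia present at entry and not worsened).* An open allowance for any baseline grade would be too broad. It could let a cycle start with, for example, grade 2 diarrhea from the disease itself, while 6.2 holds the drug for grade 2 diarrhea.

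The cost is the amendment text. No procedures, visits or patients are added.

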8. PHARMACEUTICAL INFORMATION: CAPECITABINE

within 7 calendar days of learning of the event.

Other Names: Xeloda

Chemical name: 5'-deoxy-5-fluoro-N-[(pentyloxy) carbonyl]-cytidine.

Molecular Weight: 359.35

Description: Capecitabine is a fluoropyrimidine carbamate with antineoplastic activity. It is an orally administered prodrug of 5'-deoxy-5-fluorouridine (5'-DFUR) which is converted to 5-fluorouracil.

How Supplied: Capecitabine (Xeloda) is supplied as biconvex, oblong film-coated tablets for oral administration. Each light peach colored tablet contains 150 mg capecitabine and each peach-colored tablet contains 500 mg capecitabine.

Solution Preparation: Not applicable.

Route of Administration: Oral.

Availability: Commercial supplies of capecitabine will be used for this study.

Storage and Stability: Store tightly closed at 25 degrees C (77 degrees F); stable for brief periods at 15 to 30 degrees C (59 to 86 degrees F).

8.1 Adverse events and potential risks of Capecitabine (see also tables 1 and 2)

Hand-and-Foot Syndrome: Hand-and-foot syndrome (palmar-plantar erythrodysesthesia or chemotherapy-induced acral erythema) is a cutaneous toxicity (median time to onset of 79 days, range from 11 to 360 days). This is much more commonly observed with capecitabine or infusional 5-FU rather than bolus 5-FU.

Cardiotoxicity: The cardiotoxicity observed with capecitabine includes myocardial infarction/ischemia, angina, dysrhythmias, cardiac arrest, cardiac failure, sudden death, electrocardiographic changes, and cardiomyopathy. These adverse events may be more common in patients with a prior history of coronary artery disease.

Hepatic Insufficiency: Patients with mild to moderate hepatic dysfunction due to liver metastases should be carefully monitored when capecitabine is administered. The effect of severe hepatic dysfunction on the disposition of capecitabine is not known.

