Hyperbilirubinemia: In the overall clinical trial safety database of capecitabine monotherapy (N=875), grade 3 (1.5-3 x ULN) hyperbilirubinemia occurred in 15.2% (n=133) and grade 4 (>3 x ULN) hyperbilirubinemia occurred in 3.9% (n=34) of 875 patients with either metastatic breast or colorectal cancer who received at least one dose of capecitabine 1250 mg/m² twice daily as monotherapy for 2 weeks followed by a 1-week rest period. Of 566 patients who had hepatic metastases at baseline and 309 patients without hepatic metastases at baseline, grade 3 or 4 hyperbilirubinemia occurred in 22.8% and 12.3%, respectively. Of the 167 patients with grade 3 or 4 hyperbilirubinemia, 18.6% (n=31) also had postbaseline elevations (grades 1 to 4, without elevations at baseline) in alkaline phosphatase and 27.5% (n=46) had postbaseline elevations in transaminases at any time (not necessarily concurrent). The majority of these patients, 64.5% (n=20) and 71.7% (n=33), had liver metastases at baseline. In addition, 57.5% (n=96) and 35.3% (n=59) of the 167 patients had elevations (grades 1 to 4) at both prebaseline and postbaseline in alkaline phosphatase or transaminases, respectively. Only 7.8% (n=13) and 3.0% (n=5) had grade 3 or 4 elevations in alkaline phosphatase or transaminases. In the 596 patients treated with capecitabine as firstline therapy for metastatic colorectal cancer, the incidence of grade 3 or 4 hyperbilirubinemia was similar to the overall clinical trial safety database of capecitabine monotherapy. The median time to onset for grade 3 or 4 hyperbilirubinemia in the colorectal cancer population was 64 days and median total bilirubin increased from 8 μ m/L at baseline to 13 μ m/L during treatment with capecitabine. Of the 136 colorectal cancer patients with grade 3 or 4 hyperbilirubinemia, 49 patients had grade 3 or 4 hyperbilirubinemia as their last measured value, of which 46 had liver metastases at baseline.

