13. STATISTICAL CONSIDERATIONS

13.1 Study Design/Endpoints

The primary endpoints are the PK parameters (AUC and Cmax) of capecitabine when dosed using actual versus ideal body weight. Secondary endpoints are response and progression-free survival.

A single arm study design will be used to characterize the effect on pharmacokinetic parameters of capecitabine, when dosed using actual versus ideal body weight. Ideal body with based dosing of capecitabine when be used for cycle 1 from day 1 to day 7 followed by an actual body weight based dosing from Day 9 to Day 15. There will be a wash-out period on Day 8.

PK parameters will be summarized in terms of number of observations, means, standard deviations, medians, and ranges, stratified by assessment time point. The noncompartmental method will be used to estimate PK parameters. AUC will be estimated using the Lagrange approximation method. A paired t-test will be used to compare the PK parameters between the full weight and limited weight based dosing. If the PK parameters are not normally distributed, then an appropriate transformation will be identified before conducting the comparison. The comparison of AUC and Cmax between full weight and limited based dosing will be also performed using a population pharmacokinetics analysis, based on a nonlinear mixed effects modeling approach.

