13.2 Sample Size/Accrual Rate

The primary objective is to characterize the effect on pharmacokinetic parameters when capecitabine is dosed on actual versus ideal body weight results in obese patients with advanced solid tumors. A mean difference in the AUC and Cmax of at least 30% between the ideal body weight dosing versus the actual body with based dosing will be considered as a minimal important difference. Based on the results of several previous PK studies involving capecitabine, it is anticipated that the overall standard deviation for the difference between the two dosing strategies is at most 25% of the mean difference. The following table shows the required sample sizes to detect various mean differences in PK parameters between the two dosing strategies at the two-sided 0.025 (=0.05/2 - a Bonferroni adjustment for comparing both AUC and Cmax) significance level with 80%

power, assuming a standard deviation ranging from 20-30%.

with 0070	power ai me inc	biaca 0.025 sig	infleance level				
	Mean difference in PK parameters between the ideal versus actual weight based dosing strategy						
Standard	20%	25%	30%	35%	40%		
Deviation							
20%	13	9	7	6	6		
25%	18	13	10	8	7		
30%	24	17	13	10	9		

Table 13.1: *Required sample sizes to detect various mean differences in PK parameters with 80% power at the two-sided 0.025 significance level*

A sample size of n=10 patients is proposed for this study. With a sample size of 10 patients, a clinically important difference of 30% between the ideal and actual body weight based dosing will be detected with 82% power at the one-sided 0.025 (=0.05/2 - a Bonferroni adjustment for evaluating both AUC and Cmax) significance level, assuming an overall standard deviation of 25%. A mean difference of only 25% will be detected with 68% power. Patients will be evaluable for the primary endpoint if he or she completes cycle 1, capecitabine therapy without dose reduction or skipped doses. Any patient who does not meet these criteria will be replaced.

The anticipated accrual is 1-2 patients per month. Therefore, the study is expected to be completed within 6-12 months after first accrual.

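### After toxicity on ideal-weight dosing (Days 1-8), a Day 9-15 restart one dose level lower can leave the mg dose unchanged or raise it, because Table 3 is in mg/m² and the BSA weight changes on Day 9 (minor; narrow window)

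*Combined protocol and SAP*

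**What the plan says.** - **Dose levels.** Table 3 (Section 6.1) lists 1,250, 1,000 and 750 mg/m² twice daily. It names no body weight and no mg amount.
- **Weight basis.** Section 5.1 uses ideal body weight on Days 1-7 of cycle 1, gives no drug on Day 8, and uses actual weight from Day 9 and from cycle 2. Section 13.1 repeats this: ideal-weight dosing is "followed by an actual body weight based dosing from Day 9 to Day 15".
- **Restart rule.** For grade 3-4 stomatitis and other GI toxicity, Section 6.2 says to hold until grade 1 or less, "then restart capecitabine with a dose reduction to the next lower dose level".
- **Limits on that rule.** Section 6.1 adds "Dose modification for toxicity will be based on the worst toxicity observed during the previous course". Modifications apply only to events probably or definitely due to the drug. "Toxicities which are manageable with supportive therapy" do not call for a reduction unless they persist despite maximal medical management.
- **Evaluability.** Section 13.2 counts a patient who "completes cycle 1, capecitabine therapy without dose reduction or skipped doses" and replaces the others. Section 5.6 uses a percentage-of-dose rule and says "Unevaluable patients will go off study after cycle 1".

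Nothing in Section 6 states which weight applies to a reduced dose, or requires the mg dose to fall below the one that caused the toxicity.

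**The concern.** A reduction by one Table 3 level is a 20% cut only if BSA stays the same. In cycle 1 it does not: on Day 9 the BSA input rises from ideal to actual weight in every eligible patient. If toxicity arises under the lower BSA and dosing restarts under the higher one, the two changes work against each other, and the patient may take as many mg as before, or more.

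The stake is the safety of an individual patient. The protocol's own hypothesis (Section 2.4) is that actual-weight dosing gives higher AUC and Cmax. Section 2.3 reports that 5-FU AUC rises more than in proportion to dose and is 34% higher on day 14 than on day 1. A step recorded as a reduction could therefore raise exposure in someone who has just had a severe reaction.

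**Working it through.** The plan gives no figure of its own to reproduce, so this is direct dose arithmetic.

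**Inputs.** From Section 5.1: Mosteller BSA = √(height cm × weight kg / 3600); ideal weight = 45.5 (women) or 50 (men) + 2.3 × (inches − 60); rounding to the nearest 150 mg. From Table 3: 1,250 and 1,000 mg/m². From Section 3.1.3: BMI 30 or higher, with no upper limit. The documents give no height or BMI distribution, so the grid is an assumption: every inch from 60 to 72, both sexes (26 profiles), at BMI 30, 35 and 40.

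**Ratio.** Restart dose ÷ causal dose = (1,000 × √actual) / (1,250 × √ideal) = 0.8 × √(actual/ideal). This exceeds 1 when actual/ideal is above 1.25² = 1.5625.

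**Break-even BMI** = 1.5625 × ideal weight / height².
- Woman 60 in: 1.5625 × 45.5 / 1.524² = 30.6; 72 in: 1.5625 × 73.1 / 1.8288² = 34.2.
- Man 60 in: 1.5625 × 50 / 1.524² = 33.6; 72 in: 1.5625 × 77.6 / 1.8288² = 36.3.

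**Grid results** (profile counts, not patient proportions):

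| BMI | Unrounded change | Lower / unchanged / higher after rounding, of 26 |
|---|---|---|
| 30 | −9% to −1% | 21 / 5 / 0 |
| 35 | −2% to +7% | 1 / 19 / 6 |
| 40 | +5% to +14% | 0 / 1 / 25 |

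**Examples.**
- Woman 65 in, ideal weight 57.0 kg: 1,250 mg/m² on ideal weight is 2,021 mg, given as 1,950. At 1,000 mg/m² on actual weight she gets 1,937 (given as 1,950), 2,092 (2,100) and 2,236 (2,250) mg at BMI 30, 35 and 40.
- Man 70 in, ideal weight 73.0 kg: 2,373 mg, given as 2,400. The restart dose is 2,164 (2,100, a real cut), 2,338 (2,400) and 2,499 (2,550) mg.

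**Who can enter the window.** The event must arise by Day 8, be probably or definitely attributable, and recover to grade 1 or less in time for a restart by Day 15.
- The clearest mandatory triggers in Section 6.2 are grade 3-4 stomatitis/other GI toxicity, and nausea/vomiting despite maximal medical management.
- A second grade 2 diarrhea counts only if supportive therapy cannot manage it.
- The grade 3 hematologic, hepatic and grade 3-4 diarrhea rules are permissive about resuming, and the rule for other toxicities depends on physician judgment.
- Hand-foot reaction falls outside Days 1-8: Section 8.1 gives "median time to onset of 79 days, range from 11 to 360 days". Severe hyperbilirubinemia is mostly late: "The median time to onset for grade 3 or 4 hyperbilirubinemia in the colorectal cancer population was 64 days".
- No onset times are given for stomatitis, nausea or diarrhea. Over all treatment, Tables 1 and 2 show grade 3 stomatitis in 2% (colorectal) and 7% (breast), and grade 3 nausea and vomiting in 4% each. These rates are not limited to the first 8 days, and other GI events would add to them, so they give only a rough sense of scale.

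**The case against.** **The comparator.** The Day 9 increase is the intervention. From Day 9 the planned dose is 1,250 mg/m² on actual weight, and 1,000 mg/m² is a true 20% cut from it. No rule in Section 6 is written against the previous mg dose. This is correct, and it limits the claim. But the patient has not yet taken the planned Day 9 dose; the toxicity came from the ideal-weight mg dose.

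**The previous-course sentence.** The protocol uses course to mean cycle, so reductions may be meant only between cycles. That is a fair reading, and it leaves the wording ambiguous. It does not remove the problem: a Day 9 restart would then be at full dose on actual weight, 14-24% more mg at BMI 30 and 31-43% more at BMI 40 on the grid.

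**Existing safeguards.** Section 5.3 stops treatment for unacceptable adverse events or on the investigator's judgment, and Section 5.6 takes unevaluable patients off study after cycle 1. These limit exposure but do not bar a Day 9-15 restart. The dose-discretion clause in Section 6.1 covers only events that Section 6.2 does not list.

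**Stronger readings that a reader might infer.**
- That the protocol orders a dose increase after toxicity. It does not: actual weight for the reduced dose is inferred from the dosing calendar, and at BMI 30 no grid profile rises.
- That 25 of 26 patients at BMI 40 would be affected. The grid is unweighted and describes body sizes, not the trial population.
- That the primary PK comparison is compromised. Section 13.2 already replaces patients with a reduction or skipped doses. What remains is a wording gap: Section 5.6 does not name reductions, so a Day 8 event with a reduced Day 9 start might count as evaluable there.

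**Conclusion.** The point holds as a minor one. On the hold-and-restart wording of Section 6.2, the nominal 20% reduction can be a small cut, no cut or an increase relative to the mg dose that caused the toxicity, and eligible BMIs include values where it is an increase. The arithmetic follows from the protocol's formulas. The ranges and counts rest on the assumed heights and BMIs, and the scenario rests on reading the calendar weight into the reduced dose. The documents do not allow a count of affected patients, but the timing, attribution and recovery conditions suggest few if any of 10. For most of those, exposure is limited to Days 9-15.

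**What to change.** Add to Section 6.1 or beneath Table 3: *If a toxicity arising on Days 1-8 of cycle 1 requires a hold or a reduction, any restart in cycle 1 stays on ideal body weight: 1,000 mg/m² (counted as the first reduction) where 6.2 calls for the next lower level, or 1,250 mg/m² where 6.2 says same dose level. Such patients are unevaluable for the primary PK endpoint and are replaced under 13.2.*

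After 150 mg rounding, 1,000 mg/m² on ideal weight is a 15-25% cut on the grid. It does not depend on BMI, because actual weight no longer enters. The woman of 65 in goes from 1,950 to 1,650 mg (−15%) and the man of 70 in from 2,400 to 1,950 mg (−19%). The second reduction level stays unused. The same text covers same-level restarts, such as after a first grade 2 diarrhea, which on actual weight would always raise the mg dose. It also settles evaluability between Sections 5.6 and 13.2.

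**Cost.** A short text addition; Section 5.1 already requires both BSA values. A few patients would take a lower mg dose on Days 9-15 and would not receive the planned actual-weight dose in cycle 1. They would be replaced, as Section 13.2 already requires for patients with a reduction or skipped doses.
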